Pregnancy test ¹²	X ^S	X ^{U,(S),8}							X ^{U,(S)}	X ^{U,(S)}	X ^{U,(S)}					
12 lead-ECG ¹³	X	X ⁸							X	X	X	X	X	X	X	X
Safety laboratory tests ¹⁴	X	X ^{14,8}	X	X	X	X	X	X	X ¹⁴	X ¹⁴	X					
Review of in-/exclusion criteria	X	X														

GPPGA		X	X	X	X	X	X	X	X	X	X	X	X	X	X
GPPASI		X	X	X	X	X	X	X	X	X	X	X	X	X	X

Clinical Trial Protocol

Proprietary confidential information © 2020 Boehringer Ingelheim International GmbH or one or more of its affiliated companies

FLOW CHART (CONT'D.)

Trial Period	Screening	Treatment	Follow-up Period ^{3,21}													
Visit	V1 ¹	V2 ¹	V3	V4	V5	V6	V7	V8	V9	V10 ³	V11 ³	V12 ³	V13 ³	V14/ EOS ^{2,3,24}	V15/ EOS ^{2,25}	V16/ EOS ^{2,26}
Week*			1							2	3	4	8	12	13-18	16-28
Day	-6 months to day -1	1**	2	3	4 ⁵	5 ⁵	6 ⁵	7 ⁵	8	15	22	29	57	85	92-127	113-197
Window										±3d	±3d	±3d	±7d	±7d	±7d	±7d
PSS, [REDACTED] ¹⁹		X	X	X	X	X	X	X	X	X	X	X	X	X	X	X
[REDACTED] Pain VAS, FACIT-fatigue ¹⁹		X							X	X	X	X	X	X	X	X
IRT call	X	X							X	X	X	X	X	X	X	X
Dispense/administration study drug ^{3,21}		X							X ²²							
Local tolerability ²⁰ – post dose		X							X ²²							
[REDACTED]		X	X	X	X	X	X	X	X	X	X	X	X			
Adverse events	X	X	X	X	X	X	X	X	X	X	X	X	X	X ²⁹	X ²⁹	X
Concomitant therapy	X	X	X	X	X	X	X	X	X	X	X	X	X	X	X	X
Study Completion														X	X	X
Open Label Extension Trial														X ²³		

ADA, anti-drug antibody; C, complete physical examination; [REDACTED] d, Day; [REDACTED] ECG, Electrocardiogram; EoS, end of study; FACIT-fatigue, Functional Assessment of Chronic Illness Therapy - Fatigue; Fup, Follow-up; GPPASI, Generalized Pustular Psoriasis Area and Severity Index; GPPGA, Generalized Pustular Psoriasis Physician Global Assessment; [REDACTED]; IHC, Immunohistocompatibility Complex; IRT, Interactive Response Technology; [REDACTED] Nab, neutralizing Antibodies; PK, pharmacokinetic; PRO, Patient Reported Outcome; PSS, Psoriatic Symptom Scale; RNASeq, RNA Sequencing; S, serum; T, Targeted physical examination; U, urine; V, Visit; VAS, Visual Analog Scale; Wk, week.

*Week in the flow chart represents the end of each week (e.g. End of Wk1=D8, End of Wk2 =D15, End of Wk3 = D22, End of Wk4 =D29 etc.).

**The day of first study drug administration = Day 1. All subsequent study Days are counted from this Day 1.

¹Visit 1 and Visit 2 can be on the same day if required (see also footnote 8). Initiation of randomized treatment at Visit 2 can only begin if the patient meets the criteria for Initiation of Treatment (see [Section 3.3.4](#)).

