In a multiple rising dose trial, BI 655130 or placebo have been administered to healthy volunteers at multiple ascending i.v. doses of 3, 6, 10 and 20 mg/kg given weekly for 4 weeks (i.e. 4 administrations) or a single dose of 20mg/kg (8 subjects each, 3:1 on active or PBO). Overall, multiple i.v. doses of 3 mg/kg, 6 mg/kg, and 10 mg/kg, as well as single and multiple doses of 20 mg/kg BI 655130 were found to be safe and well tolerated by the healthy male subjects in this trial. The incidence and intensity of drug related AEs appeared to be higher in the 20 mg/kg multiple dose BI 655130 treatment group than in the other treatment groups, mainly driven by headache. No dose-dependent AEs or other clinically relevant changes in safety laboratory tests, vital signs, or ECG were observed. For further details refer to the current Investigator's Brochure (IB; [c03320877](#)).

The open-label, single group phase I study trial (1368.11) was conducted to investigate the safety, tolerability, pharmacokinetics, pharmacogenomics, and efficacy of a single intravenous dose of BI 655130 (10 mg/kg) in 7 patients with acute flare of generalized pustular psoriasis. The proof-of-concept (PoC) for IL36R inhibition in GPP was achieved in these patients who showed rapid clinical responses to single administrations of BI 655130. Five of these 7 patients became clear or almost clear of GPP 1 week after the infusion, and all of them reached this status 4 weeks after treatment. Within 48 hours of treatment, pustules were completely cleared in 3 patients; pustules were cleared by Week 1 in 5 patients, and by Week 2 in 6 patients. The early response in the skin was also accompanied by an early response in systemic components (C-Reactive Protein [CRP] approaching normalization within 4 weeks). A major improvement in GPPASI was observed in all patients very early with a mean (SD) percent change from baseline of 73.2% (16.2) at Week 2; by

Week 4, this was further reduced to 82.0%, and was maintained to Week 20 (83.6%). Additional improvements (mean [SD]) from baseline to Week 2 were observed in FACIT-F, 12.3 (10.1); Pain-VAS, -45.9 (32.3); and PSS, -5.14 (3.18), all of which were also sustained through Week 4. For further details and most recent results refer to the current IB ([c03320877](#)) and published article in the New England Journal of Medicine ([P19-01888](#)).

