3. DESCRIPTION OF DESIGN AND TRIAL POPULATION

3.1 OVERALL TRIAL DESIGN AND PLAN

This is a multicenter, randomized, double-blind, placebo-controlled Phase II study with one dose of BI 655130/placebo in patients with GPP presenting with an acute flare of moderate to severe intensity. The primary objectives of this trial are to assess the efficacy, safety and tolerability of a single intravenous (i.v.) dose of BI 655130 in comparison to placebo in patients with generalized pustular psoriasis (GPP) presenting with an acute flare of moderate to severe intensity.

Approximately 11 to 20 countries will participate by using sites/centers experienced in the management of GPP.

Fifty-one patients with generalized pustular psoriasis (GPP) presenting with an acute flare of moderate to severe intensity are required to be randomized to receive BI 655130/ placebo (2:1) into this trial.

Patients are considered enrolled (screened) in the study once they have signed the informed consent.

Patients eligible to receive treatment after screening will be able to participate in this study and will be randomized at a ratio of 2:1(BI 655130/Placebo) to one of two treatment groups as shown in [Figure 3.1: 1](#). All patients will receive the first dose of study medication (900 mg i.v. BI 655130 or Placebo) on Day 1 of Week 1 (Randomization). Based on the subsequent treatment response patients will then be followed for 12 to 28 weeks (see [Flow Chart](#)). Study Week in the flow chart represents the end of each week (e.g. End of Wk1=D8, End of Wk2 =D15, End of Wk3 = D22, End of Wk4 =D29 etc.).

During Week 1, D1, D2, D3 and D8 are mandatory visits, however, D4 – D7 are optional visits and need not be attended if a patient has already achieved complete pustular clearance (GPPGA pustulation sub score =0) at the previous visit.

At the discretion of the investigator, patients may be hospitalized prior to, during or following first study drug administration. Thereafter, the decision to discharge a patient from the hospital will also be at the discretion of the investigator, based on the evolution of the GPP flare and the patient's health status.

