All days are counted relative to the day of randomized treatment, which is defined as Day 1.

^A Note that measurements made at Day 1 and assigned to the on-treatment period (because mistakenly made after start of trial treatment) via assessment on date & time (i.e. safety laboratory) will not be assigned to Day 1. Such data will be listed only.

^B Since visits 5-8 are optional, the assessments (if any) will not be displayed in tables or figures only if otherwise specified.

^C Patients who receive rescue treatment with OL Spesolimab between Wk7-Wk12 will not have scheduled V14, however if there is any unscheduled assessment between the defined extended time window for V14, it will be still used.

^D All tables and figures by visit will only report visits up to week 12 (if applicable). “Post Week 12” and “off treatment” won’t be used for any tables or figures.

^E For primary analysis visit (V9), only the assessments prior any non-randomized treatment will be used except for those pre-specified post-treatment assessments.

Repeated and unscheduled efficacy, safety and other measurements will be handled similarly to scheduled measurements and will also be assigned to a time window depending upon the date of measurement.

Notice that for EN, EN-PC and EN-ID8 estimands, any observation post intercurrent events of interests (i.e., death, escape medication or rescue medication with Spesolimab for all 3 estimands or OL Spesolimab at D8 for EN and EN-PC only) will be set to be “non-response”. Further, within the extended time window of a visit, if the day of the intercurrent event is prior to the date of planned visit, then a “non-response” observation will be assigned to that day. If the day of the intercurrent event is on or after the date of planned visit, then a “non-response” observation will be assigned to that day only if there is no other observation on the same day, otherwise, no additional observation will be assigned.

Only one observation per time window will be selected for statistical analysis at a particular visit – the value which is closest to the protocol planned visit day will be selected. If there are two observations which have the same difference in days to the planned day, but which are not measured on the same day, the later value will be selected. If there are two observations on the same day, the worst value will be selected.

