7.8.2 Laboratory data

The analyses of laboratory data will be descriptive in nature and will be based on BI standards ([8](#)). Note that data from the central Laboratory will be used for all displays described below, unless otherwise specified.

For continuous safety laboratory parameters, normalized values will be derived. Normalization means transformation to a standard unit and to a standard reference range. The process of normalization, handling of repeat values at the same visit for by-visit displays, as well as standard analyses for safety laboratory data are described in the BI guidance for the Display and Analysis of Laboratory Data ([8](#)). All analyses considering multiple times of the ULN (as described below) will be based on standardized and not normalized values. For continuous safety laboratory parameters, differences to baseline (see [Section 6.7](#)) will be calculated.

Only patients with at least one available post-baseline value will be included in the analysis of an individual laboratory parameter. All individual laboratory data will be listed. Values outside the reference range will be flagged.

Descriptive statistics of laboratory values over time and for the difference from baseline (see [Section 6.7](#)) will be based upon normalized values and provided by visit (including follow up), including the last value on treatment, the minimum value on treatment and maximum value on treatment. Graphical displays via box plots will be produced for the change from baseline, over time, for each continuous laboratory endpoint.

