Laboratory values will be compared to their reference ranges; a shift table will be provided for the number of patients with a specific RCTC grade at baseline and at the last measurement on treatment, as well as the worst grade on treatment. These analyses will be based on standardized laboratory values. Potentially clinically significant abnormalities will be identified based on BI standard rules which are based on normalized converted lab values, i.e. using SI units. These rules will be listed in the SDL appendix of the CTR. Frequency tables will summarize the number of patients with potentially clinically significant abnormalities. Patients having an abnormal lab value at baseline will be presented separately. A separate listing will present potentially clinically significant abnormal lab values; for each functional lab group all patients' lab values will be listed, if there exists at least one lab value with clinically significant abnormality within the group.

The frequency of patients with AST or ALT elevations $\geq 3\times\text{ULN}$, $\geq 5\times\text{ULN}$, $\geq 10\times\text{ULN}$, and $\geq 20\times\text{ULN}$ will be displayed based on standardized laboratory values.

To support analyses of liver related adverse drug effects, the frequency of patients with *AST and/or ALT and/or AP $\geq 3\times\text{ULN}$ plus 2 times the baseline with concomitant or subsequent total bilirubin $\geq 2\times\text{ULN}$ plus 1.5 times the baseline* in a 30 day period after AST/ALT elevation will be displayed, stratified by alkaline phosphatase $< 2\times\text{ULN}$ and $\geq 2\times\text{ULN}$ (a patient can potentially be in both alkaline phosphatase strata in case of multiple AST/ALT and bilirubin elevations). The start of the 30 day time span is triggered by each liver enzyme elevation above the defined thresholds. This analysis will be based on standardized laboratory values.

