7.8.3 Vital signs

The analyses of vital signs (blood pressure, pulse rate), body temperature, and body weight will be descriptive in nature. Descriptive statistics of vital signs over time and for the difference from baseline (see [Section 6.7](#)) will be provided, including the last value during the on-treatment period, the minimum value during the on-treatment period, and the maximum value during the on-treatment period (see [Table 6.1:1](#) for definition of the on-treatment period). Graphical displays via box plots will be produced for the change from baseline, over time, for each continuous vital sign endpoint.

[figure not shown]
Clinically relevant findings in vital signs data will be reported as baseline conditions (at screening) or as AEs (during the trial) if judged clinically relevant by the investigator, and will be analyzed as such.

[figure not shown]

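### The between-arm laboratory and vital-sign extremes rest on sample counts that depend on response, and the SAP has no balanced Week 1 table to set beside them

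*Protocol*

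**What the plan says.** Protocol 3.1 fixes the core of the first week, "During Week 1, D1, D2, D3 and D8 are mandatory visits", and then adds that "D4 – D7 are optional visits and need not be attended if a patient has already achieved complete pustular clearance". The Flow Chart footnote leaves skipping to the physician's assessment once the pustulation subscore was 0 at the prior visit. The Flow Chart marks safety laboratory tests and vital signs at each of V3 to V8 (Days 2 to 7) and at V9 (Day 8).

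SAP 7.8.2 describes laboratory values by visit, "including the last value on treatment, the minimum value on treatment and maximum value on treatment", and gives RCTC shift tables for the last measurement "as well as the worst grade on treatment". It also counts patients with a potentially clinically significant abnormality and patients with AST or ALT above multiples of ULN, and plots peak values (eDISH). SAP 7.8.3 does the same for vital signs without a grade: "the minimum value during the on-treatment period, and the maximum value during the on-treatment period".

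On the optional visits, footnote B of SAP Table 6.7: 1 says "Since visits 5-8 are optional, the assessments (if any) will not be displayed in tables or figures only if otherwise specified". It does not say whether Day 4-7 values enter the per-patient extremes.

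SAP 6.6.3 and 7.8 set the primary safety window at Day 1 to Day 85 and drop values after OL spesolimab at Day 8 or rescue spesolimab. Only the AE tables are repeated up to Week 1. No hypothesis test is planned.

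**The concern.** A per-patient minimum, maximum, worst grade or any-abnormality flag becomes more extreme as more samples are taken, even if nothing differs between arms. Here two rules make the number of samples depend on response, and they pull in opposite directions. Clearing early removes up to four samples in Days 4-7. Not clearing can lead to OL spesolimab at Day 8, after which all later values are dropped.

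Safety is part of the trial's main objective. Week 1 is the only period before OL drug can be given, so it is the cleanest randomised comparison of early laboratory and vital-sign effects. The SAP gives that period its own AE tables but no table of laboratory or vital-sign extremes. A reader of the 12-week extremes cannot tell a drug effect from a difference in how often patients were measured.

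**Working it through.** The plan states no sample count for these summaries, so there is no figure to reproduce.

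**Inputs.** From the documents:
- Post-dose visits are Days 2, 3 and 8 (mandatory), Days 4-7 (optional if clear), then Days 15, 22, 29, 57 and 85 (Flow Chart).
- The expected Week 1 clearance rates are 60% on spesolimab and 10% on placebo (Protocol 7.7).
- In the earlier open-label study of 7 patients, "Within 48 hours of treatment, pustules were completely cleared in 3 patients" (Protocol 1.2.3).
- SAP 7.5.2 expects most placebo patients to receive escape medication or OL spesolimab by Day 8, but gives no separate share for OL.

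Assumptions:
- Every patient clear by Day 3 skips Days 4-7, everyone else attends all visits, and there is no rescue.
- The share clear by Day 3 is 3/7 to 60% on spesolimab and 0 to 10% on placebo.
- The share given OL at Day 8 is 50-90% on placebo and 0-40% on spesolimab.
- The risk of an abnormal value is 5% per sample, independent unless stated.
- The five later visits apply to laboratory tests as they do to vital signs. The laboratory row of the Flow Chart is incomplete after V9 in the text available to me.
- Extra post-infusion vital signs on dosing days are not counted.

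**Step 1. Week 1, two patients.** Clear by Day 3: k = 3. Not clear: k = 3 + 4 = 7. The chance of at least one abnormal value is 1 - 0.95^k, which is 14.3% v 30.2%. With within-patient correlation 0.3 (beta-binomial) it is 10.8% v 16.9%.

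**Step 2. Week 1, arm means.** The mean is 7 - 4c, where c is the share clear by Day 3.
- Spesolimab: 7 - 4(3/7) = 5.3, down to 7 - 4(0.6) = 4.6.
- Placebo: 7 - 4(0) = 7.0, down to 7 - 4(0.1) = 6.6.

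The gap is 6.6 - 5.3 = 1.3 to 7.0 - 4.6 = 2.4 samples.

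**Step 3. Planned window to Day 85, with dropping after OL.**

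| Patient, no rescue | To Day 8 | Later, kept | Total k | 1 - 0.95^k |
|---|---|---|---|---|
| Clear by Day 3 | 3 | 5 | 8 | 33.7% |
| Uncleared, OL at Day 8 | 7 | 0 | 7 | 30.2% |
| Uncleared, no OL | 7 | 5 | 12 | 46.0% |

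**Step 4. Arm means to Day 85.** With o the share given OL at Day 8, the mean is 8c + 7o + 12(1 - c - o).
- One end: spesolimab c = 3/7, o = 0 gives 10.3. Placebo c = 0, o = 0.9 gives 7.5. Placebo minus spesolimab = -2.8.
- Other end: spesolimab c = 0.6, o = 0.4 gives 7.6. Placebo c = 0.1, o = 0.5 gives 9.1. Placebo minus spesolimab = +1.5.

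**Step 5. Two possible restrictions.**
- Mandatory visits through Day 85, still dropping values after OL: 3 + 5 = 8 for a patient clear by Day 3 v 3 for an uncleared patient given OL, or 33.7% v 14.3%.
- Days 2, 3 and 8 only, before any OL dose: 3 v 3 for everyone.

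**The case against.** The best defence is that the planned tables do not cover Week 1 alone. Over 12 weeks the two rules partly offset, the analysis is descriptive, and the defined safety endpoint is treatment-emergent AEs. By-visit summaries without V5-V8 already compare the arms at Days 2, 3 and 8. Footnote B might also be read as taking Day 4-7 values out of the extremes, and laboratory details are delegated to a sponsor guidance not supplied with the plan. Skipping is permitted, not required.

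Much of this stands. It limits the size of the problem and rules out a fixed direction. It does not remove the problem. The offset is not reliable (Step 4). By-visit summaries describe each day's distribution, not per-patient extremes or threshold counts. Footnote B concerns display, and the on-treatment minimum and maximum, taken literally, include Days 4-7.

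A reader might infer that placebo, clearing less, is sampled more and so looks less safe. That holds under these assumptions for Week 1 only, and the SAP plans no Week 1 table of these extremes. In the planned window, a patient clear by Day 3 gives 8 samples against 7 for an uncleared patient given OL drug. A reader might also take 7 v 3 as the contrast between arms. It is the largest contrast between two patients.

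**Conclusion.** The point holds as one of unequal, outcome-dependent sampling with no fixed direction. It affects minimum and maximum for laboratory values and vital signs. For laboratory values only, it also affects worst RCTC grade, clinically significant abnormality, ALT/AST threshold counts and eDISH peaks.

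The size is modest. With 3/7 of spesolimab and an assumed 5% of placebo patients skipping, and 5% risk per sample, a Week 1 table over all visits would show 23% v 29% with an abnormal value when nothing differs, or 14% v 17% at correlation 0.3. On 17 placebo patients that is about one patient (0.06 x 17 = 1.0) or less. The per-sample risk, the correlation, universal skipping and the OL shares are assumptions, and 3/7 rests on seven patients. What the documents themselves establish is the response-dependent schedule, the dropping rule, and the absence of a balanced early table.

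**What to change.** In SAP 7.8.2 and 7.8.3, before unblinding:

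- Add a between-arm table of minimum and maximum (laboratory and vital signs), worst RCTC grade, clinically significant abnormality and ALT/AST threshold counts (laboratory), restricted to Days 2, 3 and 8. Take Day 8 values before any OL dose, as footnote E of Table 6.7: 1 already requires for V9.
- Keep the planned on-treatment tables and eDISH over all visits. State that Day 4-7 values are included, so that no peak is lost. Footnote them: the number of samples depends on clearance and on OL or rescue use.
- Do not use mandatory visits through Week 12 as the main comparison, because with the dropping rule it gives 8 v 3 samples (Step 5).

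The cost is SAP wording and one extra run of existing table programs. The balanced table leaves out Days 4-7 and everything after Day 8, so it supplements the planned tables and does not replace them.

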3.2 DISCUSSION OF TRIAL DESIGN, INCLUDING THE CHOICE OF CONTROL GROUP(S)

This phase II trial with BI 655130 and placebo is to be conducted in patients with GPP presenting with an acute flare of moderate to severe intensity.

Based on data from 1368.11 which demonstrated rapid treatment onset of effect and flare resolution, a parallel group, randomized, double-blind and placebo controlled trial was considered most appropriate to evaluate the efficacy and safety of BI 655130 in patients with GPP. Also based on 1368.11 trial, the best option that can be offered for failing placebo patients is BI 655130. In the 1368.13 trial, any patients regardless of originally randomized treatment group, who experiences disease worsening and/or has recurrence of flare during the trial duration, will be offered escape treatment (SoC – physician's choice) and/or rescue treatment with open label BI 655130. Refer to [Section 3.1](#) for details regarding criteria for qualifying for escape treatment with SoC or rescue treatment with OL BI 655130.

No active control group is included in this trial as there is currently no drug approved for the induction treatment of acute flares of moderate to severe GPP. Secukinumab (Cosentyx®), infliximab (Remicade®), ixekizumab (Taltz®), brodalumab (Lumicef®), adalimumab (Humira®), guselkumab (Tremfya®) and Risankizumab are only registered in Japan for the treatment of GPP and plaque psoriasis. For secukinumab, authorization was granted on the basis of long-term treatment data (52 weeks) derived from a single open label clinical trial conducted in 12 patients with chronic GPP and an endpoint at 16 weeks ([R16-1462](#)). Moreover, due to the absence of approved drugs and a commonly accepted treatment algorithm, patients in this trial will have a very heterogenous pre-treatment history as different SoC are available in different countries, which prevents the selection of suitable active comparator which is relevant for all patients. Considering an add-on design in treatment-naïve patients or patients with a defined treatment history would make enrolment of this study non-feasible. In addition, given the lack of a known effect size for SoC treatments (e.g., biologics, retinoids, or cyclosporine), because these drugs have not been tested in clinical trials in acute GPP, the expected sample size would of necessity be much larger in an acute flare setting in order to account for potentially smaller treatment differences than might be observed in a comparable trial where placebo is used as the comparator. This approach is not feasible in a rare disease such as GPP where recruitment is much slower and driven by a population with very few patients.

Thus, study 1368-0013 will be a single-dose, placebo-controlled study of patients with acute GPP flares of moderate to severe intensity receiving 900 mg BI 655130 and then followed for an additional 12 weeks. Patients who satisfy the inclusion/exclusion criteria of subsequent open-label extension trial (1368-0025) will receive an option to continue receiving treatment for GPP with s.c. dosing. See [Section 3.1](#) for additional details on the trial design.

Please also refer to [Section 4.1.3](#) for further details.

